9. Disease status: Disease status will be evaluated every 8 weeks by history, physical examination, laboratory studies and bone marrow aspirate and biopsy as indicated by disease state and clinical parameters.
10. Rh- recipients of child bearing potential who are anticipated to receive a Rh+ product will receive Rhogam at standard dose.
11. Anti-coagulant treatment of any form (Heparin/ Warfarin/ Apixaban etc. will be withheld for one day prior to harvesting of cells from the donor
12. IAC products will meet preparation and release criteria as outlined below:
 - a. Donor leukapheresis volume will be 2.5-3.0 blood volumes or as determined by blood services.
 - b. The leukapheresis product will be appropriately labeled with: 2 patient-specific identifiers, the name of the product, the product unit number, the expiration date, donor Rh/ABO type, and the statement: "Caution: New Drug – Limited By Federal Law To Investigational Use Only".
 - c. If there is a major ABO incompatibility, the product will either be split so that no more than 10 ml ABO incompatible RBC be infused/day or undergo RBC depletion to \leq 10 ml of RBC.
 - d. The product will be transported to the [REDACTED] Hospital Transfusion Services where it will undergo irradiation (25 Gy)

according to standard operating procedures. A label indicating irradiation will be attached.

e. The product will then be assigned to the patient and the released product will be transported to and administered to the patient at [REDACTED] after pre-medication of the patient with acetaminophen 650 mg PO and diphenhydramine-HCl 25 mg PO.

d) Preliminary Data

See the research significance section above and references. IAC is an effective therapy for selected patients with renal cell carcinoma. Individual responses have also been seen in AML and CML (6, [name] personal observation). There is also evidence that allogeneic cells can induce a host CD8+ T cell response directed an AML-associated epitope (7).

e) Sample Size Justification/Statistical Analysis

The primary aim of this pilot study is to see if there is acceptable tolerance (no irreversible grade 3 or higher) experimental treatment-related serious adverse effects and any disease response for 10 patients in each cohort. This will ensure that there is at least an 80% chance that the true unacceptable rate is less than 30%. The study will be closed if there is >1 irreversible grade 3 or higher experimental treatment related adverse effect in either cohort.

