If there is (1) a steroid refractory GVHD or (2) graft failure in cohort 2, then the study will stop.

The secondary aim is to determine if there is evidence of disease response to IAC. If there is evidence of disease response in either arm, additional studies will be planned.

f) Study Variables

• *Independent Variables or Interventions*

IAC infusion every 8-12 weeks as tolerated and feasible.

Toxicity will be measured by occurrence of any experimental treatment-related Adverse Events (AE) up to 12 weeks of completion of therapy. The CTCAE Version 4.0 will be utilized for the description and grading of the AE. All symptoms, signs, or diseases assessed as experimental treatment-related will be captured and graded by a study investigator and an attribution will be associated to the experimental therapy (IAC).

Attribution of the AE:

- Definite – The AE is clearly related to the experimental therapy
- Probable – The AE is likely related to the experimental therapy
- Possible – The AE may be related to the study treatment
- Unlikely – The AE is doubtfully related to the study treatment
- Unrelated – The AE is clearly NOT related to the study treatment

Any experimental treatment-related irreversible grade 3 or higher AE (definite, probable or possible) will result in that patient not receiving any further treatment. If the AE corrects completely or to Grade 1 within 2 weeks, repeat treatment as directed by protocol may be utilized. If there is more than one such irreversible experimental treatment-related Grade 3 adverse event, the study will be terminated for that cohort.

Since a major concern is that the IAC might trigger an immune response that results in steroid-refractory GVHD OR graft failure (in cohort 2), specific parameters to diminish the likelihood of these events are included in the inclusion criteria (e.g. durable engraftment and high donor chimerism). Furthermore, the study will be terminated if even a single episode of these events occurs.

Overall response rate will be defined as the proportion of patients meeting the criteria for partial response (PR), very good partial response (VGPR) and complete response (CR). Disease response will be determined by Standards of Blood and Marrow Transplant Program disease-specific parameters.

- *Dependent Variables or Outcome Measures*

Toxicity and disease response will be measured. Disease response will use standard disease-specific parameters.

g) Drugs/Devices/Biologics

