- Patients undergoing haploidentical allogeneic hematopoietic stem cell transplants are not eligible; patients undergoing < 10/10 HLA allele matched allogeneic transplant are not eligible
- Pregnant women
- Children are not eligible as the transplant program is certified as an adult only transplant program.

(5) Subject Screening - DONOR

(a) Inclusion Criteria - DONOR

- Donor must be related to patient and be partially ($\geq 3/6$ antigen) HLA-matched.
- Donor must meet all RWJ Blood Services requirements for hematopoietic stem cell donation including:
 - Age ≥ 18 years old;
 - normal hemogram (WBC $4.0-10.0 \times 10^3/\text{mm}^3$; platelet count 150,000 to $440,000/\text{mm}^3$; Hemoglobin/Hematocrit; 12.5-18 g/dl, 38 to 54%)
 - not pregnant or lactating;
 - not HIV-1, HIV-2, HCV, Hepatitis B core or HTLV-I/II seropositive; HB S ag (-); meet other infectious disease screening criteria utilized by RWJ Blood Services;
 - no uncontrolled infections, other medical or psychological/social conditions, or medications that might increase the likelihood of patient or donor adverse effects or poor outcomes;
 - meet other blood bank criteria for blood product donation (as determined by RWJ Blood Center screening history and laboratory studies).
- Male and female and all ethnic groups are eligible provided they are fluent in English.

(b) Exclusion Criteria

- Non-English speaking person
- Pregnant women
- Children are not eligible as the transplant program is certified as an adult only transplant program.

(6) Recruitment Materials

N/A

(7) Lead Site Recruitment Methods

N/A

- **Subject Randomization**

N/A

- **Secondary Subjects**

N/A

- **Number of Subjects**

- (1) Total Number of Subjects**

A total of 20 subjects will complete the study. There will be 10 patients in each cohort. There will be a donor corresponding to each patient. There may be additional potential; donors screened if a donor fails the screening.

- (2) Total Number of Subjects If Multicenter Study**

N/A

- (3) Require Number of Subjects to Complete Research**

The number of subjects needed to complete the research procedures (i.e., numbers of subjects excluding screen failures.) is 40 (twenty patients and twenty donors). Each patient will participate in the study for 3 infusions and then be followed until disease progression or 3 years. Patients will be enrolled over a 3 year period of time.

- (4) Feasibility Of Recruiting**

We expect to enroll 7 subjects per year onto this study.

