The infusion of irradiated cells may be associated with short-term effects such as fevers, chills, dyspnea and systemic inflammatory symptoms such as shortness of breath due to pneumonia or diarrhea due to colitis. Long-term effects may include infection or autoimmunity. For patients who have received an allogeneic transplant the manifestation of "autoimmunity" might be graft-versus host disease or graft rejection.

(b) Risk Of Imposing An Intervention On Subject With Existing Condition

N/A

(c) Other Foreseeable Risks

The patients receiving therapy with IAC have very high-risk diseases and are receiving IAC as an adjuvant to transplant therapy. It may be hard to determine the toxicity related to their disease, standard treatment (transplant therapy) or the experimental therapy (IAC). In this context all patients will be at risk for infection, bleeding, organ toxicity (including heart, lung, kidney, liver, oropharyngeal, gastrointestinal, neurologic, ophthalmic and bone marrow) some of which might be irreversible and some of which could lead to long-term morbidity and death. These risks are intrinsic to the disease and standard therapy and may be worsened by the experimental therapy.

(d) Observation And Sensitive Information

N/A

(5) Minimizing Risks

The experimental intervention (IAC) involves administration of irradiated Patients receiving IAC will be reviewed weekly at 2 meetings – a weekly transplant meeting and a weekly clinical research meeting. Any SAE considered likely related to IAC will be discussed and presented for biometric evaluation re:stopping rules.

(6) Certificate of Confidentiality

N/A

(7) Potential Benefits to Subjects

IAC may improve clinical outcomes by increasing disease response rates and disease control.

(8) Provisions to Protect the Privacy Interests of Subjects

Patient confidentiality will be strictly maintained according to NIH guidelines.

(a) Research Team Access To Subject Data

The subject's personal health information, identifiers and research data are stored and kept in a secure area in the [REDACTED] computer screens containing personal health identifiers are inaccessible to public view. Only the study doctor and research team will have direct access.

c) Secondary Data – Records/Chart Reviews/Databases/Tissue Banks/etc.

[REDACTED]

20

RESERVED FOR IRB STAMP
DO NOT MODIFY THIS SPACE

Form V

Approval Date:
Expiration Date:

4/23/2021
4/22/2022

N/A

Chart/Record Review Selection

N/A

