The data collected will be stored on clinical trial management software - Oncore in Principal Investigator's computer. All Computers in OHRs are encrypted, password protected and on secured servers. Only the Principal Investigator and/or the research team will have access to the patient's data.

c) Data and Safety Monitoring

Minimal risk is anticipated however there is always the possibility of unanticipated effects. Institutional Data Safety Monitoring Board/ HROC will monitor the data from the research after initial 2-3 patients and based on their suggestions the research will be conducted as is/ Modified or discontinued.

▪ Periodic Data Evaluation

Weekly at the Blood & Marrow Transplantation and Hematologic Malignancies Tumor Study group research meetings.

▪ Type of Data Evaluated

Treatment related toxicities; unanticipated adverse events.

▪ Collection of Safety Information

Patient safety data will be reviewed at both of the above cited weekly meetings.

▪ Frequency Of Data Collection

Weekly. If there is no weekly meeting (e.g. holiday) data will be delayed until the next scheduled meeting.

▪ Reviewer of Data

Principal Investigator reviews all data.

▪ Schedule Of Review Of Cumulative Data

Review of cumulative data will occur weekly at the Hematologic Malignancies Tumor Study Group weekly research meeting.

- **Tests for Safety Data**

Weekly meetings of the Blood & Marrow Transplant Program and Hematologic Malignancies Clinical Research Tumor Study Group review each patient. Experimental treatment-related SAEs will be reported for biometric review.

- **Suspension of Research**

Suspension will take place based upon stopping rules

d) Reporting Results

- **Sharing of Results with Subjects**

Clinical results can only be shared following completion of the study.

- **Individual Results**

Patients will be notified of any abnormal findings or lab results.

- **Aggregate Results**

N/A

- **Professional Reporting**

It is expected that the results of this process will be submitted for publication in a timely manner following the conclusion. [REDACTED] all co-authors prior to submission or use, will review any abstract or manuscript.

- **ClinicalTrials.Gov Registration And Data Reporting**

The study will be registered in accordance to applicable institutional guidelines.

7) Data and/or Specimen Banking

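### The closure rule for more than one irreversible grade 3 or higher treatment-related event has two scopes: the whole study in section e, the affected cohort in section f

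*Combined protocol and SAP*

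**What the plan says.** The combined protocol and SAP states the rule twice.

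- Section e, Sample Size Justification/Statistical Analysis: "The study will be closed if there is >1 irreversible grade 3 or higher experimental treatment related adverse effect in either cohort".
- Section f, Study Variables: "If there is more than one such irreversible experimental treatment-related Grade 3 adverse event, the study will be terminated for that cohort".

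A separate rule covers a single steroid-refractory GVHD or graft failure and also appears in both sections. Section e has "If there is (1) a steroid refractory GVHD or (2) graft failure in cohort 2, then the study will stop"; section f has "the study will be terminated if even a single episode of these events occurs".

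Elsewhere the protocol only points back to these rules. Under Minimizing Risks: "Any SAE considered likely related to IAC will be discussed and presented for biometric evaluation re:stopping rules". Under Suspension of Research: "Suspension will take place based upon stopping rules". Under Data and Safety Monitoring, the institutional board reviews early data ("HROC will monitor the data from the research after initial 2-3 patients") and may have the research modified or discontinued, but nothing there says which scope applies.

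**The concern.** After two qualifying events in one cohort, section e as written closes the study, while section f ends it for the affected cohort and is silent on the other. The weekly meetings and the biometric review are asked to apply the stopping rules, and they have two texts to choose from.

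Two groups in the other cohort depend on the answer: patients still to enter, and patients already enrolled who are due further infusions (up to three, 8 to 12 weeks apart, under Treatment Plan item 4). Letting them go on breaches the literal text of section e. Stopping them goes further than section f asks.

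**Working it through.** **The two texts side by side**

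| | Section e | Section f |
|---|---|---|
| Trigger | more than one irreversible treatment-related event, grade 3 or higher | more than one such event, called Grade 3 |
| Where counted | in either cohort | in the cohort concerned |
| What ends | the study | the study, for that cohort |

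The grade wording is a minor difference. In section f the word *such* refers back to grade 3 or higher earlier in the same paragraph. The real difference is the last row. Section f limits the consequence to a cohort for this rule and leaves it unlimited for GVHD or graft failure a paragraph later, so within that section the qualifier carries meaning.

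**The plan's own figure**

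Section e claims at least an 80% chance that the unacceptable rate is below 30%, with 10 patients per cohort. The closure rule tolerates at most one event in 10. The exact binomial confidence that the rate is below 30% is then P(X ≥ 2 | n = 10, p = 0.30) = 85.1%; with no events it is 1 − 0.7^10 = 97.2%. The claim reproduces and does not depend on the scope.

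**Chance of closure under each scope**

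Inputs: 10 patients per cohort (Number of Subjects). Assumptions: the event rate p, because the protocol gives none; independent cohorts; at most one event per patient.

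One cohort reaches two events with probability q = 1 − (1 − p)^10 − 10p(1 − p)^9. At p = 0.10, q = 1 − 0.3487 − 0.3874 = 0.2639. A given cohort closes with probability q under the cohort scope and 1 − (1 − q_A)(1 − q_B) under the study-wide scope.

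| Rate in both cohorts | Cohort scope | Study-wide scope |
|---|---|---|
| 5% | 8.6% | 16.5% |
| 10% | 26.4% | 45.8% |
| 20% | 62.4% | 85.9% |
| 30% | 85.1% | 97.8% |

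With 5% in one cohort and 30% in the other, the safer cohort closes with probability 8.6% under the cohort scope and 1 − 0.9139 × 0.1493 = 86.4% under the study-wide scope.

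**How often the texts would part during accrual**

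Assume patients enter A, B, A, B and so on, with events known at once. Let f(k) = (k − 1)p²(1 − p)^(k − 2) be the probability that a cohort's second event falls on its kth patient, and S(k) the probability of fewer than two events in k patients. The texts part while at least one patient is still to enter the other cohort with probability

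Σ f(k)S(k − 1) over k = 2 to 10 (A first) + Σ f(k)S(k) over k = 2 to 9 (B first).

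| Rate | A first + B first | Total | Mean still to enter the other cohort (of 10) |
|---|---|---|---|
| 5% | 0.0829 + 0.0683 | 15.1% | 3.8 |
| 10% | 0.2334 + 0.1963 | 43.0% | 4.2 |
| 20% | 0.4518 + 0.3843 | 83.6% | 5.2 |
| 30% | 0.5328 + 0.4380 | 97.1% | 6.2 |

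A simulation of 400,000 trials gives 15.1%, 43.0%, 83.5% and 97.1%.

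Delay lowers these figures. Feasibility Of Recruiting says "We expect to enroll 7 subjects per year onto this study", which is one patient every 52/7 = 7.4 weeks. If each event becomes known 24 weeks after entry, the totals are 9.9%, 30.9%, 71.0% and 91.6%. At 48 weeks they are 7.6%, 24.7%, 62.2% and 86.2%. Enrolled patients still due infusions are not counted in any of these.

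**The case against.** The strongest reply is that the two sentences can be obeyed together. Section f does not say the other cohort continues, and closing the whole study also ends the affected cohort. Section e could equally be a summary in which *either cohort* sets a per-cohort count and section f supplies the consequence; the sample size is, after all, justified per cohort. Both readings are possible. They lead to opposite actions for the other cohort, though, and the protocol does not say which to use. *In either cohort* might even be read as a pooled count over 20 patients, which at a 10% rate would close the study with probability 60.8%.

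Three narrower objections stand.

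- The contrast in wording with the GVHD and graft-failure rule exists only in section f. Section e writes *the study* for both rules and so draws no distinction.
- At high rates the other cohort often closes on its own events anyway. Under the same accrual assumptions, the probability that the texts part and the other cohort never reaches two events is S(10) × [q + (q − f(10))]. This gives 14.4%, 36.0%, 44.6% and 24.7% at rates of 5%, 10%, 20% and 30%. At 30% the scope therefore changes whether the other cohort finally closes in only about a quarter of the divergent trials (24.7/97.1), although it still changes when that cohort closes.
- The event rates and the strict alternation of cohorts are assumptions, and 5% against 30% is a deliberately wide contrast.

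None of this removes the conflict. It limits how much weight the figures at high rates can bear.

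**Conclusion.** The concern holds. Two current sentences attach different consequences to the same safety trigger on the primary endpoint, and nothing else in the protocol settles which governs. This must be fixed before the rule has to be used.

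The consequence is material at modest event rates. At 10% in both cohorts, the choice of text moves a given cohort's chance of closure by 45.8 − 26.4 = 19.4 percentage points. All the probabilities rest on assumed rates, independent cohorts and one event per patient; the accrual figures also rest on alternating entry. The contradiction itself rests on none of these. The threshold and the 80%/30% justification are sound under either scope.

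**What to change.** The sponsor should reconcile sections e and f to one closure scope and state it in identical words in both, including whether events are counted per cohort and the same grade wording (section e has grade 3 or higher, section f's closing sentence has Grade 3). Which scope applies is for the sponsor to decide; this review does not propose one. The references to stopping rules under Minimizing Risks and Suspension of Research should then cite that single text.

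The cost is a wording change in two sections and two cross-references. Sample size and study procedures do not change.

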Registration: Once a potential donor has been identified for respective patient, both the patient / recipient and the relative/ donor will sign consent to participate in the study. Upon signing the consent, donor will undergo protocol mandated screening for eligibility. Once donor's eligibility is confirmed both patient and donors will be registered for the study by OHRS research staff.

Each participant will be given a unique identifier code. No patient will start treatment prior to registration.

All eligible patients will be treated at [REDACTED] and receive standard treatment per Blood & Marrow Transplant Program Policies.

1. Patients in cohort 1 will be treated initially with IAC within 42 days after hematopoietic engraftment (both neutrophils and platelets). Engraftment is

defined by 3 consecutive measurements with absolute neutrophil count > 500/mm³ and platelets > 20,000/mm³ without transfusion.

2. Patients in cohort 2 with *high-risk* disease will be treated initially with IAC within 120 days after hematopoietic engraftment (neutrophils and platelets). Chimerism studies must reveal engraftment of donor CD3+ cells > 80% and there must not be any evidence of > grade I *acute* GVHD or *severe* chronic GVHD, per standard CIBMTR staging.
3. Patients in cohort 2 being treated for *relapsed* disease may receive initial treatment with irradiated allogeneic cells any time after relapse documented. They may receive disease specific therapy prior to the experimental cell therapy, but they must have recovered from the disease-specific therapy prior to the experimental cell therapy.
4. All treated patients who do not have evidence of relapse or progressive disease may be treated q 8-12 weeks for up to 3 treatments with delays up to 8 weeks as clinically indicated.
5. Donor will undergo evaluation at RWJ Blood Services within 7 days of each infusion.
6. Donors meeting eligibility requirements will be harvested by leukapheresis with targeted CD3+ (0.5-3.0 x 10⁸/kg); harvesting will be done according to FACT and AABB guidelines.
7. Donor cells (0.5-3 x 10⁸ CD3+/kg) will be irradiated (25 Gy) and infused no more than 24 hours after harvesting of the cells; in case of ABO incompatibility either RBC depletion will be undertaken or the product will be split to assure infusion of \leq 10 ml ABO incompatible RBC/day.
8. Management of cytopenias, infections, and other complications will conform to standard procedures at the discretion of the physician.

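### Outside steroid-refractory GVHD or graft failure in cohort 2, no rule requires a dosing hold or a DSMB/HROC decision when an IAC-related death occurs

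*Combined protocol and SAP*

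**What the plan says.** Four provisions decide what happens after a related event.

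- **General rule, section 1(e):** "The study will be closed if there is >1 irreversible grade 3 or higher experimental treatment related adverse effect in either cohort".
- **First event, section 1(f):** "Any experimental treatment-related irreversible grade 3 or higher AE (definite, probable or possible) will result in that patient not receiving any further treatment".
- **Restatement of the general rule, section 1(f):** "If there is more than one such irreversible experimental treatment-related Grade 3 adverse event, the study will be terminated for that cohort".
- **Exception, section 1(f):** for steroid-refractory GVHD or graft failure in cohort 2, "Furthermore, the study will be terminated if even a single episode of these events occurs".

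Section 6(c), Data and Safety Monitoring, adds that suspension follows the stopping rules. It brings in the institutional DSMB/HROC after the first 2-3 patients, with the research then continued, changed or stopped on its advice. It provides for weekly review at the transplant and tumor study group meetings, gives review of all data to the Principal Investigator, and sends related SAEs to biometric review. Under Risks to Subjects, (5) Minimizing Risks describes that biometric step as an evaluation against the stopping rules.

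Dosing is partly discretionary. Section 1(f) gives "IAC infusion every 8-12 weeks as tolerated and feasible", and Treatment Plan item 4 says that patients without relapse or progression "may be treated q 8-12 weeks for up to 3 treatments with delays up to 8 weeks as clinically indicated". First infusions are tied to windows. Item 1 reads "Patients in cohort 1 will be treated initially with IAC within 42 days after hematopoietic engraftment", and item 2 sets 120 days for high-risk patients in cohort 2. Item 7 requires cells to be "infused no more than 24 hours after harvesting of the cells".

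**The concern.** Ending the affected patient's treatment is an empty consequence when the event is a death. The general rule asks nothing for any other patient until a second event occurs in the same cohort.

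The plan already treats one steroid-refractory GVHD or graft failure in cohort 2 as enough to stop the whole study. A related death by another route, including any in cohort 1, triggers neither a stop nor a pause. The protocol itself names other routes of concern: hypotension, pulmonary infiltrates, autoimmunity, and immune activation with organ damage.

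Toxicity is the primary objective. Under Risks to Subjects, (4)(c) accepts that IAC toxicity may be hard to separate from that of disease or transplant, and that IAC may worsen risks that can lead to death. This is where a recorded decision by a body outside the treating team is most useful before anyone else is dosed.

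**Working it through.** **1. The plan's own figure.** Section 1(e) claims at least an 80% chance that the true unacceptable rate is below 30%, with n = 10 per cohort. With at most one event in 10, 1 − P(X ≤ 1 | 0.30) = 1 − (0.7^10 + 10 × 0.3 × 0.7^9) = 1 − (0.028 + 0.121) = 0.851. With no events, 1 − 0.7^10 = 0.972. With two events it falls to 0.617. The claim therefore holds for 0 or 1 event and agrees with a rule of more than one. The sample-size figure is not in question.

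**2. The rules applied case by case.** Death is not named in the general rule. It is taken here as an irreversible grade 3 or higher event.

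| Related events | Required under 1(e) | Required under 1(f) |
|---|---|---|
| One death, either cohort | Nothing for other patients | Nothing for other patients |
| One death in each cohort (2 of 20) | Nothing: the count is 1 per cohort | Nothing: the count is 1 per cohort |
| Two deaths in one cohort | Study closes | That cohort closes; no hold or review for the other |
| One steroid-refractory GVHD or graft failure, cohort 2 | Study stops | Study terminated |

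The last row sits in the same two sections as the general rule and is consistent between them. The third row is not.

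**3. Illustration of size.** From the documents: 10 patients per cohort. Assumed: independent cohorts, full enrolment, at most one event per patient, and per-patient risks d (related death), q (non-fatal irreversible grade 3+ related event) and g (steroid-refractory GVHD or graft failure, cohort 2 only). Let s = 1 − d − q − g. For each cohort:

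- A = P(no rule met) = s^10 + 10(d + q)s^9
- B = P(no rule met and no death) = s^10 + 10q·s^9
- P(at least one death, no rule met) = A1·A2 − B1·B2
- P(exactly one death in each cohort, no rule met) = product over cohorts of 10d·s^9

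Worked case, d = 5%, q = g = 0: A = 0.5987 + 0.3151 = 0.9139 and B = 0.5987, so 0.9139² − 0.5987² = 0.477. One death in each: 0.3151² = 0.099.

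Worked case, d = q = g = 5%: A1 = 0.7361, B1 = 0.5424, A2 = 0.4285, B2 = 0.3127, so 0.7361 × 0.4285 − 0.5424 × 0.3127 = 0.146.

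| Assumed d | 1% | 5% | 10% | 15% |
|---|---|---|---|---|
| At least one death, no rule met (q = g = 0) | 17% | 48% | 42% | 26% |
| Same, q = g = 5% | 6% | 15% | 11% | 6% |
| One death in each cohort, no rule met (q = g = 0) | 0.8% | 10% | 15% | 12% |
| Same, q = g = 5% | 0.2% | 2% | 3% | 2% |
| Exactly one cohort has two or more deaths (q = g = 0) | 0.9% | 16% | 39% | 50% |

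The last row is 2A(1 − A); at 10%, 2 × 0.7361 × 0.2639 = 0.39. It counts full enrolment in both cohorts. It shows that the case where 1(e) and 1(f) disagree is at least as likely as one death in each cohort at every assumed risk.

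The first four rows are end-of-study outcomes. They include a death after which nobody remains to be dosed, and they leave out a first death followed by a second event that meets a rule.

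**The case against.** A two-event rule per cohort, with single-event stops for the most feared complications, is a coherent pilot design. Weekly review would see any death within days. Section 6(c) sends related SAEs to biometric review without limiting that review to the stopping rules. The board sentence can be read as monitoring that starts after 2-3 patients and continues. Repeat dosing is permissive, so investigators can pause. IAC is given under an IND, and outside procedures may apply. The general rule counts adverse effects, not patients, so one fatal course with two irreversible grade 3+ related events might meet it alone. The text of (5) Minimizing Risks also breaks off mid-sentence, so a claim that wording is absent there needs caution.

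Much of this stands and limits the point. A reader might infer that the plan leaves a related death unreviewed, or has patients dosed regardless. The documents do not support that: the death would be discussed, and the team and the board could act. A reader might also infer that the stopping threshold is miscalibrated, but the 80%/30% statement reproduces.

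What does not answer the point is that each safeguard permits action and none requires it. The weekly meetings belong to the treating programs. On either reading of the board sentence, its role is tied to a patient count and no available text ties it to a death. The documents describe no IND procedure triggered by a death. The first-infusion windows carry no stated allowance for a hold.

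**Conclusion.** The point holds as a specific monitoring gap that should be closed. A related death outside the cohort 2 exception requires no hold and no board decision. One death in each cohort meets no rule. On 1(f)'s wording a second event closes one cohort and leaves the other without review.

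That last part depends on which section governs. One might read the plan as settled on cohort-only closure, but 1(e) closes the study, and the documents do not resolve the difference. Per-cohort counting is the better-supported reading, because 1(f) ties termination to the cohort.

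The percentages are illustrations, not estimates of the risk in this trial. The documents give no related-death risk, the 5% competing risks are assumed, and nothing here measures how many patients a hold would protect. Confidence is medium.

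**What to change.** In 1(e)/(f) and 6(c), add wording such as:

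> At each death judged definitely, probably or possibly related to IAC, in either cohort, new registrations, donor collections and all IAC infusions are held in every cohort not already closed, including when the death itself closes the other cohort. The hold lasts until the DSMB/HROC has reviewed related deaths and irreversible grade 3+ related events in both cohorts together and recorded a decision to continue, modify or stop, with a target of 14 days. A product already collected is not infused unless the board clears it within 24 hours of harvest. The 42-day and 120-day first-infusion windows are extended by the length of the hold, and repeat infusions use the 8-week delay already allowed.

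Also state, in the same words in 1(e) and 1(f), whether more than one event closes the study or only that cohort. The single-event GVHD/graft-failure rule stays as it is.

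**Cost.** A few sentences, using the existing board. If more than one event closes the study, at most two holds can occur, one per cohort. If it closes only the cohort, a third is possible in the cohort still open, plus any for later related deaths among patients already treated in the closed cohort.

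At the planned 7 subjects per year, a 14-day hold in both cohorts affects 7 × 14/365 = 0.27 new patients. If everyone receives three infusions (14 repeats a year), it affects 14 × 14/365 = 0.54 repeat infusions. An assumed 8-week overrun affects 1.1 and 2.1. With at most 21 products a year, the chance that one is within its 24 hours when a hold starts is about 21/365 = 6%.

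Some holds will follow deaths later judged due to disease or transplant; the documents give no basis for a rate. Donor evaluations done within 7 days of an infusion may need repeating.
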